## **9.4 Data sources**

KPNC is an integrated health care delivery system providing health care to over 3.8 million members with 3,300 physicians, 32 outpatient clinics and 17 hospitals. Analysis of U.S. census data demonstrates that KPNC members are representative of the population living in the served geographic area. KPNC maintains medical information on each patient through a computerized

EHR database called “Health Connect” since 2007. Therefore, we have access to high quality clinical data.

Admitting, Discharge and Transfer (ADT) System. A complete database on all hospitalizations at any KPNC hospital since 1971 is maintained with data that are highly comparable to the UB-92 forms (required of all hospitals in California and most other States), and contains a principal and up to 12 secondary discharge diagnoses and codes for up to seven procedures for each hospitalization. Admitting and discharge diagnoses and procedures are coded according to the International Classification of Disease, 9th revision (ICD-9). The accuracy of principal discharge diagnoses obtained from Kaiser Permanente databases has been verified in other studies.

The Laboratory Utilization and Reporting System (LURS) is a clinical database that captures all laboratory tests and results performed at the Kaiser Permanente of Northern California regional laboratory since 1991. In 1995, LURS incorporated all hospital-based laboratories of Northern California. Providers use this system to order tests, obtain results and share them with patients. Thus, data in LURS are of higher quality than a chart review study could achieve (since chart review involves small rates of reviewer and transcription error). LURS contains patient name, medical record number, test name (each test has a unique code), date, and result. Essentially all thyroid tests ordered are available in the LURS database.

Outpatient Service Clinical Record (OSCR), a computerized database, will be a source to identify outpatient diagnosis of thyroid disorders.

The database contains a unique identifier for all information on all drugs issued to patients, all hospitalizations, captured with ICD-9 coding, outpatient diagnoses and laboratory tests and result. KPNC membership is stable and more than 97% of members have 5 or more years of membership.

## **9.5 Study Size**

Around 2300 children exposed to iodinated contrast agent among all pediatric patients.

## **9.6 Data management**

Data management will be conducted at KPNC where a data set of all children under age 4 will be created. From this database children exposed to iodinated contrast will be identified and followed for a year to detect hypothyroidism. Researchers at KPNC in collaboration with BU researchers will review electronic records to ensure data validity. All primary data will be held at KPNC. Further details can be found in the DMP.

## **9.7 Data analysis**

Incidence density rates will be calculated using person-time of follow up. Baseline characteristics of the cases with hypothyroidism and of the rest of the cohort as well as the time-relation between iodine contrast exposure and diagnosis of hypothyroidism will be described using descriptive statistics. This will be done for all hypothyroidism cases and separately for the “probable iodine induced” category and the “possible alternative etiology” category. In the “probable iodine induced” category we will further ascertain the duration of the hypothyroidism episode.

If sample size and number of hypothyroidism cases allows, joint associations between possible risk factors and hypothyroidism will be examined in a multivariate statistical model (e.g. age, sex, bodyweight, type of procedure)

CCI

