### 4. Abstract

**Title:** Study of Iodinated contrast agents and risk of hypothyroidism in young children in the United States

**Rationale and background:** While it is generally known and acknowledged that exposure to iodine contrast can interfere with thyroid function, little is known about the incidence of iodine-induced hypothyroidism in young children (under age 4).

**Research question and objectives:** The goal of this study is to estimate the incidence rate of detected hypothyroidism in a US-based general population of patients less than 4 years of age during years 2008 - 2015, who were exposed to an iodinated contrast agent.

**Study design:** This will be a retrospective cohort study.

**Population:** Patients less than age 4 in the US-based *Kaiser Permanente Northern California* data during years 2008 through 2015

**Variables:** Age, sex, calendar year, diagnostic procedure, comorbidities, treatments

**Data sources:** *Kaiser Permanente Northern California* database

**Study size:** There are millions patients under age 4 in the *Kaiser Permanente Northern California* database. From these data we expect to identify around 2300 pediatric patients who had a diagnostic procedure with an iodinated contrast agent.

**Data analysis:** We will estimate incidence rates of hypothyroidism in the 365 days post exposed procedure. We will also describe these patients according to characteristics, comorbidities, treatments, and diagnostic procedure received, as well as the time-relation between contrast exposure and hypothyroidism

**Milestones:** A preliminary report will be provided by December 2016 and a final report by 31 March, 2017

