## 7. Rationale and background

It is generally accepted that iodinated contrast agents can cause thyroid dysfunction because of the free iodide in the contrast solution. While a typical dose of 100 ml of contrast agent with an iodine concentration of 300 mg iodine/ml contains 30 g of bound iodine, the same solution also contains unbound or free iodine. Typical values of free iodide present in contrast material are

CCl

. The actual amount of free iodide administered to a patient depends on the total dose, concentration and time between production of contrast agent and use.

Excessive free iodide may inhibit thyroid hormone synthesis, causing hypothyroidism through an acute Wolff-Chaikoff effect. Normal thyroid hormone synthesis typically resumes after the acute Wolff-Chaikoff effect is corrected. Because neonates have immature thyroid tissue, they are especially susceptible to the Wolff-Chaikoff effect. Since it is known that thyroid hormones are essential for the development of newborn and infants, hypothyroidism may pose a serious threat to a child's physical and mental development if left untreated. Hypothyroidism can affect both newborns and older children and can lead to delayed growth, overweight, enlargement of the thyroid gland, among other symptoms. In very young children prolonged hypothyroidism can lead to development delay.

The incidence of hypothyroidism after exposure to iodinated contrast agents is unknown in this patient population. In a literature review by Ahmet et al. nine studies were analyzed examining the effects of iodinated i.v. contrast media on thyroid function of neonates. Overall 8.3% of the term infants and 18.3% of the premature infants developed hypothyroidism after iodinated contrast media exposure; suggesting that preterm infants have an increased risk of hypothyroid compared to term infants. The authors noted that all studies were highly affected by bias. A retrospective database-study in a mainly adult patient population reported that iodinated contrast media exposure was associated with incident hyperthyroidism (odds ratio [OR], 1.98; 95% CI, 1.08-3.60), while no statistically significant association with incident hypothyroidism was observed (OR, 1.58; 95% CI, 0.95-2.62) (Rhee et al, Arch Int Med, 2012). In secondary analyses

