## **8. Research questions and objectives**

### **8.1 Primary objective**

The goal of this study is to estimate the incidence rate of hypothyroidism, detected in routine clinical practice, in a US-based general population of patients less than 4 years of age during years 2008 - 2015, in the 365 days post exposure to an iodinated contrast agent. .

Hypothyroidism cases will be categorized into “probable iodine-induced hypothyroidism” and “possible alternative etiology” after medical records review.

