### **9.3.2 Exposure**

Exposure will be identified through CPT codes for procedures that include iodinated contrast agent. The date the procedure was coded will be considered the date of exposure. The majority of these will be CT scans with contrast. We will also identify young children who had a left heart catheterization including cardio-angiography, ventriculography, and coronary angiography. Each child will be followed for up to 365 days after a qualifying exposure (the exposure window).

There will be no differentiation according to any specific brand of contrast agents, considering that there is general agreement that iodine induced hypothyroidism is considered a class-effect of all iodinated contrast agents and not restricted to specific agents

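### The only incidence measure visible in the plan is one person-time rate over up to 365 days; for an effect described as acute, add cumulative incidence at set days and time-banded rates, with intervals

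*Combined protocol and SAP*

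**What the plan says.** The measure is set in section 9.7: "Incidence density rates will be calculated using person-time of follow up". The abstract has the same target, "We will estimate incidence rates of hypothyroidism in the 365 days post exposed procedure", and section 8.1 fixes the period as "in the 365 days post exposure to an iodinated contrast agent". Section 9.3.3 asks for rates for all cases together and for each of the two etiology categories. Sections 8.2 and 9.7 also plan to describe the time from exposure to diagnosis, and the length of the episode in probable iodine-induced cases.

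No cumulative incidence, rate by time since exposure, or interval method appears in the visible text. A redacted block follows the analysis text in 9.7, so further detail may exist there.

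On mechanism, section 7 says: "Excessive free iodide may inhibit thyroid hormone synthesis, causing hypothyroidism through an acute Wolff-Chaikoff effect". It adds that hormone production usually recovers afterwards. On prior evidence it reports: "Overall 8.3% of the term infants and 18.3% of the premature infants developed hypothyroidism after iodinated contrast media exposure", and notes that the reviewed studies were all judged highly biased.

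On follow-up, section 9.2.3 requires membership for only 2 weeks after exposure, and section 9.3.2 allows up to 365 days. Table 1 in section 6 ends data collection in November 2016.

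**The concern.** Events divided by person-time summarise a year well when the hazard is roughly constant. The mechanism in section 7 points the other way: if contrast causes hypothyroidism acutely, any excess should come early and the remaining months should carry mainly background cases. One figure for the year then does not show when the risk occurs.

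There is a second consequence. When events cluster early and children leave later, the events stay in the numerator while late person-time drops out of the denominator. The rate rises with loss to follow-up although the risk has not changed. Follow-up is not guaranteed to be complete: a child may leave after 2 weeks, and one exposed in December 2015 cannot have a full year by November 2016. The visible text of 9.7 gives no rule for death, disenrolment or data end.

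What is at stake is whether a reader can tell from the report how likely a child is to be diagnosed in the first weeks after contrast, as opposed to at any time in the following year.

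**Working it through.** **Figure in the plan.** Section 9.5 gives only "Around 2300 children exposed to iodinated contrast agent among all pediatric patients". This is a database count with no expected rate or precision target behind it, so there is nothing to reproduce. It is used below as N = 2300. Section 9.2.3 shows that it comes from a preliminary search, before the exclusions.

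**Assumptions not in the documents.** Onset is uniform over 30, 90 or 365 days. Risk is 1%, 8.3% or 18.3%; the last two are the cited neonatal proportions, used only as test values. Yearly loss is 0, 3, 20 or 50%, with none before day 14 and exponential loss afterwards.

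**Formulas with no loss**, for risk p and onset window w days:

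- Events = N × p
- Person-years over 365 days = N × [365 − p(365 − w/2)] / 365.25
- Person-years within the window = N × w(1 − p/2) / 365.25

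Example with p = 0.083 and w = 30:

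- Events = 2300 × 0.083 = 190.9.
- Year: 2300 × (365 − 29.05)/365.25 = 2115 person-years, so 9.02 per 100.
- Window: 2300 × 30 × 0.9585/365.25 = 181.1 person-years, so 105.4 per 100.
- Ratio = 105.4/9.02 = 11.7.

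| Risk | Onset window (days) | Events | Person-years | 365-day rate per 100 | Rate in window per 100 | Ratio |
|---|---|---|---|---|---|---|
| 1% | 30 | 23.0 | 2276 | 1.01 | 12.2 | 12.1 |
| 1% | 90 | 23.0 | 2278 | 1.01 | 4.1 | 4.0 |
| 1% | 365 | 23.0 | 2287 | 1.01 | 1.0 | 1.0 |
| 8.3% | 30 | 190.9 | 2115 | 9.02 | 105.4 | 11.7 |
| 8.3% | 90 | 190.9 | 2131 | 8.96 | 35.1 | 3.9 |
| 8.3% | 365 | 190.9 | 2203 | 8.67 | 8.7 | 1.0 |
| 18.3% | 30 | 420.9 | 1895 | 22.21 | 245.2 | 11.0 |
| 18.3% | 90 | 420.9 | 1930 | 21.81 | 81.7 | 3.75 |
| 18.3% | 365 | 420.9 | 2088 | 20.16 | 20.2 | 1.0 |

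The ratio is close to 365/w (12.2 for 30 days, 4.1 for 90), so it restates the assumed window. It is not evidence about when onset occurs.

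**Dependence on follow-up.** True risk 8.3%; 365-day rate per 100 person-years:

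| Yearly loss | Onset within 30 days | Onset over 365 days |
|---|---|---|
| 0% | 9.02 | 8.67 |
| 3% | 9.15 | 8.66 |
| 20% | 9.95 | 8.65 |
| 50% | 12.08 | 8.62 |

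With onset spread over the year, loss hardly moves the rate. With early onset it does. Converting the 50% figure back to a risk with the constant-hazard formula gives 1 − exp(−0.1208) = 11.4%, against a true 8.3%.

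**What the planned timing description can give.** It summarises days to diagnosis among cases. Risk by day t also needs the number of children still followed and free of the event at t, which a case-only summary does not carry.

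**Precision, for illustration.** For 23 cases in 2300 person-years the rate is 10.0 per 1000, with an exact Poisson 95% interval of 6.3 to 15.0, or 0.63 to 1.50 times the estimate. That relative width depends on the case count, so a band with fewer cases will have a wider interval.

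**The case against.** The strongest reply is that section 9.7 matches its objective. Section 8.1 asks for an incidence rate over 365 days, and over a one-year window such a rate is nearly the one-year risk. With loss of 0 to 3%, a risk of 8.3% gives 8.7 to 9.2 per 100 person-years, and 18.3% gives 20.2 to 22.5. Section 9.4 reports that more than 97% of members have at least 5 years of membership. Background cases are partly separated by the etiology classification, and timing and duration will be described. If loss is low, early cases divided by cohort size come close to early risk. The documents give no onset distribution, and the days chosen for time bands have no source in them. Cases are also dated by routine detection, so narrow bands partly reflect when children were tested.

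Most of this stands and limits the point. A reader might infer that the planned rate understates the risk of hypothyroidism. It does not: no case is lost, and in these calculations the rate lies slightly above the one-year proportion. A reader might also infer that the result cannot be set against 8.3% and 18.3% because one is a rate and the others are proportions. With near-complete follow-up that difference is small. The larger obstacles are that the cited figures come from neonates, in studies described as highly biased, whereas this cohort is under 4 years and cases are found in ordinary care. Cumulative incidence alone would not remove those.

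Two parts of the reply do not settle the matter. The membership figure describes members in general; a child under 4 cannot yet have 5 years of membership at exposure. And dividing early cases by cohort size is sound only if loss is low, which the plan does not commit to showing.

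**Conclusion.** The point holds as a low-cost improvement to the analysis. In the visible text a single person-time rate is the only incidence measure. Given the acute mechanism in section 7, that rate probably averages unequal periods, and it moves with loss to follow-up when onset is early.

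The size depends entirely on assumed onset: about 4-fold averaging of the early rate for a 90-day window, 11- to 12-fold for 30 days (1% to 18.3% risk, no loss), and none if onset is spread over the year. The effect on the apparent one-year level is small at 0 to 3% loss and reaches 12.1 per 100 person-years for a true 8.3% only at an assumed 50% loss with 30-day onset.

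It would go too far to say that the plan ignores timing, since it describes time to diagnosis and duration, or that it has no interval method at all, since the redacted block in 9.7 may contain one.

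**What to change.** In section 9.7, keep the 365-day rate and add, overall and for the probable iodine-induced category:

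- Cumulative incidence at prespecified days, for example 30, 90 and 365, by an Aalen-Johansen estimator with death as a competing event and with disenrolment and data end as censoring.
- Rates by time since exposure, for example days 0–30, 31–90 and 91–365, with the person-time in each band.
- 95% intervals: exact Poisson for rates, log-log for cumulative incidence.

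If any comparison with the cited 8.3% and 18.3% is made, show neonates or infants separately and repeat the caveat about bias in the source studies. Section 9.3.1 does not name gestational age, so a comparison for premature infants would depend on prematurity being captured among the comorbidities.

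The cost is a few lines of text and standard software on the same data. Short windows will have wider intervals, and the report should say that dates reflect routine testing and may lag true onset.

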## **9.8 Quality control**

At the BCDSP/BU epidemiologists will work closely with our KPNC collaborators to ensure correct clinical definitions and data integrity. All analyses will be performed by trained epidemiologists familiar with large electronic health databases. We have procedures for checking data to be sure that the data have been correctly identified and classified. That is, we will check the characteristics of the study population to be sure they meet the study criteria by reviewing a random sample of electronic case records (“profiles”). We will create cross tabulations to describe the characteristics (including age, sex, comorbidities) of the study population and compare the results to the limited available epidemiology literature of hypothyroidism in young children and exposure to iodine in US youth. We will do data checks to confirm that person time was correctly calculated, and we will review the full electronic patient record to validate cases of

hypothyroidism and we will also abstract information from the patients complete medical records to validate all cases.

## **9.9 Limitations of the research methods**

There is access to original clinical records in the KPNC database, thus validation will be possible. However we may miss some children who had procedure using iodinated contrast if the procedures were not coded properly. It is also possible that some children will have undiagnosed hypothyroidism. These will also be missed in this study.

Although most members enroll through their employers, many are members of KPNC through MediCal (a low-income health insurance plan). Analysis of U.S. census data demonstrates that KPNC members are representative of the general population with regard to ethnicity and education and differ only slightly with regard to income, we tend to underrepresent the very rich and the very poor. Members are remarkably similar to the general population in terms of employment status, marital status, screening practices, and prevalence of medical conditions, when compared with population-based data from the California Behavioral Risk Factor Surveillance System.

## **9.10 Other aspects**

None noted

## **10. Protection of human subjects**

Data will be derived from a large de-identified database (KPNC) and the study will go through the PPD review process to ensure protection of all patients involved.

## **11. Management and reporting of adverse events/adverse reactions**

As per the EMA Guideline on Good Pharmacovigilance Practices (Module VI–Management and reporting of adverse reactions to medicinal products), for non-interventional study designs that are based on secondary use of data, individual reporting of adverse reactions is not required. Reports of adverse events/reactions will be summarized in the study report (European

Medicines Agency 2012).

## **12. Plans for disseminating and communicating study results**

Results will be provided to Bayer Pharma AG in a preliminary report no later than March 2017.

Study results will be published following guidelines of the International Committee of Medical Journal Editors (ICMJE, 2013), and communication in appropriate scientific venues will be considered.

When reporting results of this study, the appropriate STROBE checklist (STROBE, 2007) will be followed.

### **Annex 1. List of stand-alone documents**

Number	Document reference number	Date	Title
1	None	Sep 2016	

Annex 2. ENCePP checklist for study protocols (Revision 2, amended)

Adopted by the PPD on 14/01/2013; Doc.Ref. EMA/540136/2009

**Study title:**

Iodinated contrast agents and risk of hypothyroidism in young children in the United States

**Study reference number:**

TBD

Section 1: Milestones	Yes	No	N/A	Page Number(s)
1.1 Does the protocol specify timelines for				
1.1.1 Start of data collection 				6
1.1.2 End of data collection 				6
1.1.3 Study progress report(s)				6
1.1.4 Interim progress report(s)				6
1.1.5 Registration in the EU PAS register				6
1.1.6 Final report of study results.				6

Comments:

Section 2: Research question	Yes	No	N/A	Page Number(s)
2.1 Does the formulation of the research question and objectives clearly explain:				
2.1.1 Why the study is conducted? (e.g. to address an important public health concern, a risk identified in the risk				

 Date from which information on the first study is first recorded in the study dataset or, in the case of secondary use of data, the date from which data extraction starts.

 Date from which the analytical dataset is completely available.

Section 2: Research question	Yes	No	N/A	Page Number(s)
management plan, an emerging safety issue)				
2.1.2 The objective(s) of the study?				7-8
2.1.3 The target population? (i.e. population or subgroup to whom the study results are intended to be generalised)				8
2.1.4 Which formal hypothesis (-es) is (are) to be tested?				
2.1.5 If applicable, that there is no a priori hypothesis?				
				

Comments:

Section 3: Study design	Yes	No	N/A	Page Number(s)
3.1 Is the study design described? (e.g. cohort, case-control, randomised controlled trial, new or alternative design)				9
3.2 Does the protocol specify the primary and secondary (if applicable) endpoint(s) to be investigated?				9
3.3 Does the protocol describe the measure(s) of effect? (e.g. relative risk, odds ratio, deaths per 1000 person-years, absolute risk, excess risk, incidence rate ratio, hazard ratio, number needed to harm (NNH) per year)				13

Comments:

Section 4: Source and study populations	Yes	No	N/A	Page Number(s)
4.1 Is the source population described?				9

Section 4: Source and study populations	Yes	No	N/A	Page Number(s)
4.2 Is the planned study population defined in terms of:				
4.2.1 Study time period?				9
4.2.2 Age and sex?				9
4.2.3 Country of origin?				9
4.2.4 Disease/indication?				10
4.2.5 Co-morbidity?				
4.2.6 Seasonality?				
4.3 Does the protocol define how the study population will be sampled from the source population? (e.g. event or inclusion/exclusion criteria)				9

Comments:

--

Section 5: Exposure definition and measurement	Yes	No	N/A	Page Number(s)
5.1 Does the protocol describe how exposure is defined and measured? (e.g. operational details for defining and categorising exposure)				9
5.2 Does the protocol discuss the validity of exposure measurement? (e.g. precision, accuracy, prospective ascertainment, exposure information recorded before the outcome occurred, use of validation sub-study)				11
5.3 Is exposure classified according to time windows? (e.g. current user, former user, non-use)				10
5.4 Is exposure classified based on biological mechanism of action and taking into account the pharmacokinetics and pharmacodynamics of the product?				7
5.5 Does the protocol specify whether a dose-dependent or duration-dependent response is measured?				

Comments:

--

Section 6: Endpoint definition and measurement	Yes	No	N/A	Page Number(s)
6.1 Does the protocol describe how the endpoints are defined and measured?				10-11
6.2 Does the protocol discuss the validity of endpoint measurement? (e.g. precision, accuracy, sensitivity, specificity, positive predictive value, prospective or retrospective ascertainment, use of validation sub-study)				11

Comments:

--

Section 7: Confounders and effect modifiers	Yes	No	N/A	Page Number(s)
7.1 Does the protocol address known confounders? (e.g. collection of data on known confounders, methods of controlling for known confounders)				11
7.2 Does the protocol address known effect modifiers? (e.g. collection of data on known effect modifiers, anticipated direction of effect)				11

Comments:

--

Section 8: Data sources	Yes	No	N/A	Page Number(s)
8.1 Does the protocol describe the data source(s) used in the study for the ascertainment of:				
8.1.1 Exposure? (e.g. pharmacy dispensing, general practice prescribing, claims data, self-report, face-to-face interview, etc.)				11 - 12
